#### Table 4 Tablet description

Name	Туре	Description	Main functionalities
Tablet	Commercial device (CE)	Smart tablet	Main functionalities: Opening and navigating the digital platform for healthcare professionals. Visualizing and using Dialogg app by participants

#### 5.3. Description of platform

The platform developed by Tellu represents an advanced technology infrastructure RPM facilitating the transition of care from the hospital to the home. Designed to provide personalized and secure healthcare, the platform integrates telehealth, alarm management and remote supervision services, offering complete interoperability with medical devices and other healthcare systems through the adoption of open standards. At the core of the platform is a data repository compliant with the HL7 FHIR standard, which enables structured organization and management of patients' clinical information. This repository collects and stores health profiles, treatment plans, measurements acquired through medical devices, and responses to self-assessment questionnaires. This data is accessed through an architecture of modular APIs designed to meet

the specific needs of each type of user. The Dialogg mobile application allows patients to interact with the system, recording measurements and communicating with healthcare professionals. Healthcare providers, on the other hand, use a dedicated web interface to monitor clinical parameters, manage alerts and update care plans. Platform administration is provided by specific tools for user, device and data security management. On the sensitive information protection front, an advanced authentication and security system based on OpenID Connect and OAuth 2.0 is implemented, with strict role management and an encryption system that complies with international ISO 27001 standards and European GDPR regulations. Every transaction is recorded in an audit log to ensure traceability and transparency in data access. A distinctive feature of the platform is its ability to integrate certified medical devices and physical activity tracking systems. With Bluetooth device compatibility, the system captures vital data such as blood pressure, blood glucose, body temperature, and oxygen saturation. In parallel, integration with Fitbit allows monitoring of parameters related to physical activity and sleep quality, providing a complete picture of the patient's health status. The collected data are transmitted and stored in the FHIR database, used for advanced processing based on machine learning, thus enabling timely intervention in case of abnormalities. Further adding value to the platform is its integration with Memas, a digital assistant designed to support patients in the daily management of their health. Through interactive tools, Memas provides educational materials, general suggestions on diet and exercise, as a "disease literacy" information system. No coaching intervention are meant to be performed with the platform.

For Italian participants, the information collected in Memas and provided to the end user are generic guidelines released by Italian National Healthcare Societies (ISS, Ministero della salute) and International healthcare organizations (WHO). Moreover, self-assessment questionnaires will be available in the system, which allow the patient's well-being to be monitored and any critical issues to be reported to health care providers. TelluCare provides the secure and scalable technology infrastructure for managing health data, while Memas enriches the patient's experience, fostering autonomy in managing their own health and improving communication with caregivers. Further detail and specification of digital platform characteristics are reported in Sec 3 of D2.1.

# 6 Study endpoints

### 6.1. Primary endpoint

The primary endpoint of the study is constituted by the reduction of the incidence of 30-days rehospitalization rate, supporting the self-management of the patients through an innovative remote monitoring system. It will be accessed by checking if the older adult is readmitted in the healthcare facility at the end of the 30 days trial period.

### 6.2. Secondary endpoints

The secondary endpoints are:

- Checking hospital readmission at 60 and 90 days after hospital discharge to evaluate longer term rates.
- Checking how many times the participant possibly got re-hospitalized.
- Improving health status of older person in terms of general quality of life and physical performance. It
  will be accessed through EQ Visual Analogue Scale [26] and Short Form Health Survey 12 items [27] for
  general wellbeing status and Short Physical Performance Battery [23] for physical performance and
  functional status;
- Accessing the usability of the system, to be evaluated through the System Usability Scale [28] to check specific dashboard usability
- Supporting the empowerment of participants in terms of digital/eHealth literacy skills achievement, skills that will be assessed through eHeals scale [29].
- Evaluate acceptability, usability, effectiveness and willingness to pay of the system through semistructured interviews;
- Evaluation of clinical resource utilization through interviews.

# 7 Protocol

For this pilot study, 210 older adults will be enrolled. The participants will be randomized into 2 groups, respectively 105 cases and 105 controls. The randomization technique based on a single sequence of random assignments is used

A summary of all data collected and when these are collected is provided in Table 5. All scales used are validated in all the national languages of each end-user partner (Italian, Norwegian and Romanian) and suitable for administration for the patients recruited in the study. A complete list of scales are attached as Appendix to the present deliverable.

Scale(s)	R	то	T1	Т2	Т3
Socio-demographic and Anamnesis (Check-list)	$\checkmark$				
MMSE (cognitive)	$\checkmark$				
Short Physical Performance Battery (physical)	$\checkmark$		$\checkmark$	$\checkmark$	$\checkmark$
Clinical Frailty Scale (Frailty)	$\checkmark$				
30-days Rehospitalization rate (y/n)			$\checkmark$		
60-days Rehospitalization rate (y/n)				$\checkmark$	
90-days Rehospitalization rate (y/n)					$\checkmark$
ATDPA – C (Technology attitude)		$\checkmark$			
EQ-5D-5L (only VAS scale) (quality of life)		$\checkmark$	$\checkmark$	$\checkmark$	$\checkmark$
SF-12 short form (4 weeks recall period) ( impact of health in everyday life)		$\checkmark$	√		~
Clinical resource utilization			$\checkmark$	$\checkmark$	$\checkmark$
SUS (Usability of dashboard)			$\checkmark$		$\checkmark$
eHEALS scale (ehealth literacy)		$\checkmark$	$\checkmark$		$\checkmark$
Semi-structured interview on self-management improvement, usability and effectiveness of the system			√		$\checkmark$

Table 5 Clinical assessments and scales divided by different evaluation times

The **Mini Mental State Examination (MMSE)** [22] is a neuropsychological test used to assess cognitive function and detect cognitive impairment; it is particularly useful for monitoring the development of dementia and assessing the cognitive status of patients in clinical settings. Consisting of 30 questions, the test assesses five areas: orientation, registration, attention and computation, recall, language and visuo-constructive skills. The maximum score is 30, with scores below 24 indicating possible cognitive impairment.

The **Short Physical Performance Battery (SPPB)** [23] assesses physical performance based on three criteria by testing balance, walking speed and chair raising abilities. This scale is a valuable tool for assessing physical function, especially in older adults and individuals with chronic conditions. Because of its simplicity, reliability, and clinical utility, the SPPB is an essential tool for assessing physical function and improving health management in the older person and vulnerable populations.

**Clinical Frailty Scale (CFS)**. [24] This descriptive scale divides the older participants into 9 classes based on the information provided by them and their relatives: between 1 and 3 the patient is non-frail, pre- frail if 4, he/she is frail from 5 to 9.

The Assistive technology device predisposition assessment (ATD PA-C) [25] module is the user's module that analyzes the user's subjective satisfaction with the results achieved in a variety of functional areas. It is part of the ATD PA (Assistive technology device predisposition assessment) tool and asks the user to prioritize aspects of his or her life where improvements are desired and solicits the user's perspective with respect to the aid.

The **EuroQol Visual Analogue Scale (EQ VAS)** [26] records the respondent's self-rated health on a 20 cm vertical, visual analogue scale with endpoints labelled 'the best health you can imagine' and 'the worst health you can imagine'. This information can be used as a quantitative measure of health as judged by the individual respondents.

The **Short Form Health Survey - 12 items (SF-12)** [27] is a self-assessment questionnaire designed to measure health-related quality of life quickly and concisely. It is an abbreviated version of the SF-36, with only 12 items that provide a broad assessment of physical and mental health conditions.

The **System Usability Scale (SUS)** [28] is a reliable tool for measuring usability. It consists of a 10-item questionnaire with five response options for respondents, from 'Strongly agree' to 'Strongly disagree'. It allows for evaluation of a wide variety of products and services, including hardware, software, mobile devices, websites and applications. It is easy to administer to participants and can be used onsmall sample sizes with reliable results and can effectively differentiate between usable and unusablesystems.

The **eHealth Literacy Scale (eHEALS)** [29] is a 10-item measure of eHealth literacy developed to measure consumers' combined knowledge, comfort, and perceived skills at finding, evaluating, and applying electronic health information to health problems. Advantages include simplicity and speed, in fact it is a short and easy test to administer, suitable for clinical and research settings; user focus, as it focuses on perceptions and subjective abilities, allowing for identification of specific educational needs; and flexibility, as it can be adapted to different populations and cultural contexts.

A **Semi-structured Interview** is adopted to evaluate the perspective on usability, acceptability, effectiveness and willingness to pay. A complete version of interviews is included in the material to be delivered to Ethical Committee for approval.

A **Clinical Resource Utilization** will be used to investigate consumption of health care resources, use of diagnostic tests and specialized clinical procedures, use of care services, and eventual hospital readmission, throughout the study period.

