
#### Visual Analogue Scale (VAS)

#### Health Status - SF-12

«This survey asks for your views about your health. This information will help keep track of how you feel and how well you are able to do your usual activities. Please answer carefully every question. Some questions may look like others, but each one is different».

(FOR THE INTERVIEWER: Pay attention that the subject answer to all questions, otherwise the test is not valid and the total score cannot be calculated.)

1. «In general, would you say your health is»:

Excellen t	Very good	Good	Fair	Poor
5	4	3	2	1

«The following questions are about activities you might do during a typical day. Does your health now limit you in these activities? If so, how much?»

	Yes, limited a lot	Yes, limited a little	No, not limited at all

 
Moderate activities, such as moving a table, pushing a vacuum cleaner, bowling, or shopping
 
	1	2	□3
3. Climbing several flights of stairs	1	2	3

«During the past week, have you had any of the following problems with your work or other regular daily activities as a result of your physical health?»

	Yes	No
4. Accomplished less than you would like	1	0
5. Were limited in the kind of work or other activities	1	0

«During the past week, have you had any of the following problems with your work or other regular daily activities as a result of any emotional problems (such as feeling depressed or anxious)?»

	Yes	No
6. Accomplished less than you would like	1	0
7. Did work or other activities less carefully than usual	1	0

8. «During the past week, how much did pain interfere with your normal work (including both work outside the home and housework)?»

Not at all	A little bit	Moderately	Quite a bit	Extremely
1	2	3	4	5

«These questions are about how you feel and how things have been with you during the past week. For each question, please give the one answer that comes closest to the way you have been feeling»

«How much of the time during the past week...»

	All of the time	Most of the time	A good bit of the time	Some of the time	A little of the time	None of the time
9. Have you felt calm and peaceful?	1	□2	□3	4	□5	6
10. Did you have a lot of energy?	□1	□2	□3	4	□5	6
11. Have you felt downhearted and blue?	1	 2	□3	4	□5	6

12. «During the past week, how much of the time has your physical health or emotional problems interfered with your social activities (like visiting friends, relatives, etc.)?»

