All of the time	Most of the time	A good bit of the time	Some of the time	A little of the time
1	2	3	4	5

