8. «During the past week, how much did pain interfere with your normal work (including both work outside the home and housework)?»

Not at all	A little bit	Moderately	Quite a bit	Extremely
1	2	3	4	5

«These questions are about how you feel and how things have been with you during the past week. For each question, please give the one answer that comes closest to the way you have been feeling»

«How much of the time during the past week...»

	All of the time	Most of the time	A good bit of the time	Some of the time	A little of the time	None of the time
9. Have you felt calm and peaceful?	1	2	□3	4	5	6
10. Did you have a lot of energy?	□1	□2	□3	4	□5	6
11. Have you felt downhearted and blue?	 	2	□3	□4	□5	6

12. «During the past week, how much of the time has your physical health or emotional problems interfered with your social activities (like visiting friends, relatives, etc.)?»

All of the time	Most of the time	A good bit of the time	Some of the time	A little of the time
1	2	3	4	5

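### Table 5 specifies a 4-week SF-12, but all three attached SF-12 forms ask about the past week, and item 12 as printed has no answer for a participant with no interference

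*Protocol*

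**What the plan says.** Section 6.2 measures quality of life, as part of the health-status secondary endpoint, with the "EQ Visual Analogue Scale [26] and Short Form Health Survey 12 items [27]". Table 5 in Section 7 schedules the second of these at T0, T1 and T3 and fixes its recall: "SF-12 short form (4 weeks recall period)". The same section says that "A complete list of scales are attached as Appendix to the present deliverable", and that all scales are validated in Italian, Norwegian and Romanian.

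The Appendix prints the SF-12 three times, under T0, T1 and T3. Items 4 to 7 open with "During the past week, have you had any of the following problems with your work". Item 8 reads "During the past week, how much did pain interfere with your normal work". Items 9 to 11 share a stem that also refers to the past week. Item 12 begins "During the past week, how much of the time has your physical health or emotional problems" and offers five answers, the last being "A little of the time". Each form tells the interviewer to obtain an answer to every question, "otherwise the test is not valid and the total score cannot be calculated".

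**The concern.** The recall period is part of the definition of a patient-reported outcome. Table 5 names one period and the attached forms ask about another, so a team cannot comply with both. If the forms are used as printed, the data are not those that Table 5 describes, and this cannot be repaired after collection because the participant was never asked about the other three weeks.

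Item 12 is a separate defect on the same page. If the printed list is what participants see, someone with no interference must either report a little interference or leave the item blank. The first cuts off the healthy end of the item, where improvement would show. The second loses the total score under the form's own rule.

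**Working it through.** No power or sample size figure bears on this point. The check sets Table 5 beside the forms and adds simple window arithmetic.

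**1. Which items have a recall window.** Items 1 to 3 ask about health in general or about present limitation and have none. Items 4 to 12 do: 12 − 4 + 1 = 9 of 12 items.

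**2. Recall specified and recall printed.**
- Table 5, for T0, T1 and T3: 4 weeks = 4 × 7 = 28 days.
- Appendix T0 form, items 4 to 12: past week = 7 days.
- Appendix T1 form, items 4 to 12: past week = 7 days.
- Appendix T3 form, items 4 to 12: past week = 7 days.

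The 4-week recall appears on none of the three forms. Share of the specified window covered: 7 / 28 = 25%.

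**3. What this means at T1.** T1 is at 30 days. A 4-week recall covers 28 / 30 = 93% of the interval, and a one-week recall covers 7 / 30 = 23%. With 4 weeks, T1 summarises nearly the whole primary follow-up period. With one week, it describes only the end of it.

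**4. Whether 4 weeks could be a slip in Table 5.** The documents do not say which place is in error. Most sections of the Clinical Resource Utilization form, used at T1, T2 and T3, ask about the past 4 weeks, so that window is at least in use elsewhere in this trial.

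**5. Item 12 beside items 9 to 11.**
- Items 9 to 11, on all three forms: six answers coded 1 to 6, the sixth being *None of the time*.
- Item 12, on all three forms: five answers coded 1 to 5, running from all of the time to a little of the time.

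The missing answer is the one that denotes no interference. Together with the completeness rule on the form, this leaves such a participant two routes: an untrue answer or no total score.

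**The case against.** **The item 12 gap may come from reading the PDF.** Text extracted from the file loses answer options elsewhere in the Appendix: the 30-day rehospitalization item shows only a No box and the 60-day item shows none, while the 90-day item shows both. Against this, item 12 shows the same five labels with codes 1 to 5 three times, and the six-column table just above it survives each time. A true form error is the more likely explanation, but the source form has to be checked. The recall wording is running text, so the doubt does not reach it.

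**Participants may answer national-language versions.** Those versions are not in the protocol, so the documents establish a contradiction between Table 5 and the attached forms, not what each patient will read. That stands as a limit. It also means that the check must be made in each language.

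**The same form at every visit keeps change comparable.** This is true within a participant, but the change is still over a different window from the one specified, and a truncated item 12 would remain truncated throughout.

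**Stronger readings that the documents do not support.**
- A reader might infer that the SF-12 cannot be scored as planned. The protocol states no scoring algorithm, so there is none to contradict; only the form's completeness rule and the option list can be relied on.
- A reader might infer that both arms are affected at all three visits. Section 8.1 says that controls are simply checked for rehospitalization, and Section 8.2 limits the T1 assessments to the experimental group and does not name the SF-12. Collection from controls after T0 is therefore unclear.
- A reader might infer that a one-week form at T0 mostly describes the hospital stay. Section 8.1 places recruitment before discharge or within 3 days of it, but T0 is not dated exactly and no length of stay is given.
- A reader might expect some sites to follow Table 5 and others the Appendix. Section 8.1 says that procedures are the same at all sites, so this is a possibility and not something the documents show.

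**Conclusion.** The contradiction on recall holds: 9 of the 12 items, on all three attached forms, ask about 7 days where Table 5 specifies 28. This rests on Section 7's statement that the scales are those in the Appendix.

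The item 12 defect holds for the form as printed, subject to a check of the source. Its effect on the endpoint cannot be sized from the documents, because nothing indicates how many participants would report no interference. Section 4.2 describes the typical Italian and Norwegian patient as frail, so the number could be small.

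The SF-12 is one of several secondary measures. The primary endpoint and the sample size are untouched. The point should nevertheless be settled before the first form is completed, since neither the recall window nor a missing answer category can be recovered later.

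**What to change.** Before first use:

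1. Choose one recall version. Either replace the three Appendix forms with the 4-week version that Table 5 names, or amend Table 5 to one week.
2. Use that version, and the scoring that belongs to it, at every site and every visit.
3. Check item 12 against the source form in Italian, Norwegian and Romanian. If *None of the time* is absent there too, add it, so that a participant without interference can answer truthfully.
4. While Table 5 is open, state whether controls complete the SF-12 at T1 and T3, and bring Sections 8.1, 8.2 and 8.4 into line.

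The cost is one questionnaire swap, or one edited table row, and a notification to the ethics committees. No visits are added.

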# 8 Procedure

# 8.1. Recruitment (R) and Baseline Evaluation (TO)

Recruitment and experimentation procedures are the same among the three European pilot sites. Patient will be enrolled from the operative unit/facility department, listed below:

- Geriatrics Acute Care Ward of IRCCS INRCA, in the Ancona branch, according defined inclusion criteria.
- Medical and Geriatric Departments at Sørlandet Hospital Health Trust, Flekkefjord, and the allocation of services department of municipality of Farsund according to defined inclusion criteria.
- Cardiology Department of the 'Niculae Stancioiu' Heart Institute, in Cluj-Napoca, according to the defined inclusion criteria.

During the recruitment phase (R), i.e., prior to discharge or within 3 days of discharge, general information will be collected about the subjects, particularly health status and cognitive condition. MMSE will be administered to gain a cognitive level framework, the CFS to evaluate frailty and SPPB to access physical condition.

The investigator will contact (by mail, telephone or physically) the participant to define his availability with a view to setting up the research project at home and will access his/her signed consent. When recruitment is complete, the investigator will randomize the participants into two groups: control group and experimental group. The allocation is done in an alternating randomized manner (ABAB) according to the order of inclusion of the participants. Participants in the experimental group will receive the digital platform already installed in a tablet (Table 4), or alternatively, they will use their own smartphone. In this case, they will be helped with the installation of the application and advised on how to use it. Furthermore, they will receive a set of medical/non-medical devices as reported in Table 2 and Table3. Participants in control group will not be assigned any type of technology but will simply be checked whether they will be re-hospitalized at the end of 30, 60, or 90 days.

At the staring of the experimentation, baseline evaluation (T0) is conducted directly at the hospital or at patient's home according to specific local needs of each end-user partner. The scales included Sociodemographic questionnaires, ATDPA-C, EQ-5D-5L VAS, SF-12 and eHEALS, will be administered.

The participant belonging to experimental group will receive training sessions about the digital platform and the medical/non-medical device utilization.

During the first month of experimentation, the participant belonging to the experimental group will be invited to use the devices in the way he/she wishes. In any case, participants will not be obliged to manipulate the devices.

In addition, during the experimentation phase, participants will be contacted weekly to inquire about the utilization experience and their feelings about the activity and, possibly, offer technical help when needed.

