# 4 Study design, setting and population

The general objective is to measure the 30-day re-hospitalization rate in patients with different conditions characterized by a high risk of re-hospitalization. This will be achieved by using an ecosystem of home devices and a central monitoring platform on 210 older adults recruited from Italy, Romania and Norway. Each country will enrol different number of subjects, as reported in Table 1.

Each end-user partner will recruit population in specific recruiting centre, as reported below:

- Institutul Inimii "Nicolae Stancioiu", [name]
- IRCCS INRCA, [name]
- Farsund kommune, [name]

Table 1 Experimental trial participants divided by country

Older adults					
Italy Romania					Norway
Case	Controls	Case	Controls	Case	Controls
50	50	15	15	40	40
100		30			80

The pilot study involves three different phases: Recruitment (R), Baseline evaluation (TO), final evaluation 30 days after discharge (T1), first follow-up 60 days after discharge (T2) and second follow-up 90 days after discharge. At 60 and 90 days, patients will continue to use the technology to evaluate the effect of the ecosystem on the other two re-hospitalization outcomes. For this reason, "follow-up evaluations" have been defined. Figure 2 summarizes the pilot study design of Italian trial.

Figure 2 Pilot study design of TransCare Italian trial

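### Allocation is described both as a random sequence and as predictable ABAB alternation by the enrolling investigator role, which leaves the readmission comparison open to steering

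*Protocol*

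**What the plan says.** Section 7 presents the trial as randomised: "The participants will be randomized into 2 groups, respectively 105 cases and 105 controls". It names the method in one sentence: "The randomization technique based on a single sequence of random assignments is used".

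Section 8.1 gives the operating procedure. The same role makes the approach and obtains signed consent: "The investigator will contact (by mail, telephone or physically) the participant to define his availability". That role then allocates: "When recruitment is complete, the investigator will randomize the participants into two groups: control group and experimental group". The rule follows directly: "The allocation is done in an alternating randomized manner (ABAB) according to the order of inclusion of the participants".

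MMSE, CFS and SPPB belong to the recruitment phase, which runs up to three days after discharge. The ATDPA-C, EQ VAS, SF-12 and eHEALS belong to T0, which section 8.1 describes after the allocation paragraph: "At the staring of the experimentation, baseline evaluation (T0) is conducted directly at the hospital or at" the patient's home. Controls receive no technology, so the arm is evident once assigned. The protocol describes neither concealment of the next assignment nor an independent holder of the list.

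**The concern.** A random sequence and a fixed ABAB pattern are different designs, and a site cannot follow both. The procedure section is the one that staff will work from, and its pattern makes the next arm certain. The word for randomisation inside that sentence does not help, because order of inclusion fixes everything after the first assignment.

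This matters because of what the enrolling staff already know. Frailty, cognition and physical performance are recorded before allocation, and the introduction (section 1) itself ties frailty to re-hospitalisation. Someone who knows that the next slot is technology can delay or discourage a frail patient, or one who seems unlikely to cope with devices, until a control slot comes up. Such a shift lowers readmission in the technology arm without any treatment effect. The confounder-adjusted regression in section 9 cannot be relied on to remove it, since the steering may rest on clinical impressions that nobody records.

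A second and smaller exposure concerns self-reported baselines. If T0 follows allocation, as the order of section 8.1 suggests, participants may rate their health and eHealth literacy already knowing whether they will receive the system.

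**Working it through.** **1. Predictability of the next assignment**

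| Scheme | Chance of guessing the next arm correctly |
|---|---|
| ABAB, one assignment known | 100% |
| Simple random sequence | 50% |
| Unmasked fixed blocks of 4 / 6 / 8, best guessing | 71% / 68% / 67% |

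Section 8.1 sits in the first row. Section 7, on its natural reading, does not. The block figures show why the recruiter should not know the block size either.

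**2. The plan's own figure**

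Inputs from section 9: 19.3% v 5.2%, two-sided Fisher exact test, alpha 0.05, power 0.85, 103 per arm. With b(x; n, p) the binomial probability,

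power = Σᵢ Σⱼ b(i; n, p_T) · b(j; n, p_C), summed over tables with Fisher p ≤ 0.05.

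This gives 0.849 at 102 per arm, 0.852 at 103 and 0.860 at the planned 105. The stated 206 reproduces, and 1:1 concealed randomisation does not change it.

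**3. What steering could do to the primary test**

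The documents give no risk mix and no steering rate, so both are assumed here. Let 25% of eligible patients have a 40% readmission risk and the other 75% a 12.4% risk. The overall risk is 0.25 × 0.40 + 0.75 × 0.124 = 0.193, which matches the control rate in section 9. There is no true effect. An arm with a share h of high-risk patients has risk 0.124 + 0.276 h.

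Let s be the fraction of high-risk patients due for technology who are steered to control. Two cases bound who takes the vacated slot:

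- Case A, a low-risk patient fills it: h_T = 0.25(1 − s), h_C = 0.25(1 + s).
- Case B, the next arrival fills it and is steered at the same rate: h_T = 0.25(1 − s)/(1 − 0.25 s), h_C = 0.50 − h_T.

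For s = 1/4, case B gives h_T = 0.1875/0.9375 = 0.200. For s = 1/2, it gives 0.125/0.875 = 0.143.

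The last column applies the sum from step 2 at 105 per arm, counting only tables with fewer readmissions in the technology arm.

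| s | Case | h_T / h_C | Risk, technology v control | False significant benefit |
|---|---|---|---|---|
| 0 | – | 25.0% / 25.0% | 19.3% v 19.3% | 1.7% |
| 1/4 | B | 20.0% / 30.0% | 17.9% v 20.7% | 5.2% |
| 1/4 | A | 18.8% / 31.3% | 17.6% v 21.0% | 6.7% |
| 1/2 | B | 14.3% / 35.7% | 16.3% v 22.3% | 14.8% |
| 1/2 | A | 12.5% / 37.5% | 15.9% v 22.8% | 19.4% |

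The 1.7% is half of the Fisher test's true two-sided size of 3.3% at this risk.

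**4. Which measures the T0 order could touch**

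From Table 5 (section 7) and section 8.1:

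- 30-day readmission has no baseline, so it is not touched.
- SPPB has its baseline at recruitment, before allocation, so it is not touched.
- ATDPA-C is taken once, so it has no change score.
- SUS has no baseline.
- EQ VAS, SF-12 and eHEALS have T0 baselines and later repeats, so they are exposed.

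**The case against.** **Control of enrolment is spread out.** The investigator is a role, not one person. Section 4.2 has a physician or nurse screening in Italy and a shared hospital–municipal process in Norway, where the municipal office is notified of all potential patients. The three-day limit after discharge also restricts how long anyone can be held back. This weakens the idea that a single individual screens, consents and allocates, and the protocol does not show that. Steering becomes harder but not impossible: the pattern is visible to anyone who sees the last allocation, and several eligibility items need judgement.

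**Allocation might happen after the whole cohort is recruited.** Recruitment closes within three days of each discharge and the endpoint runs from discharge, so recruitment being complete must mean each participant's own recruitment. Order of entry would determine the arm on either reading.

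**It is called a pilot.** Section 9 nevertheless powers a between-arm test at 0.85, so a comparative conclusion is intended.

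**Readings that go too far.** A reader might infer from "Table 1 Experimental trial participants divided by country" that the exact 50/50, 15/15 and 40/40 splits are incompatible with one random sequence. Table 1 gives planned numbers, and missing them by chance would be no error. ABAB within each site would meet them. The table shows only that the text should say whether allocation is by country. A reader might also infer that patients certainly know their arm at T0, or that every change-from-baseline comparison is biased. The protocol does not state the first, since only paragraph order suggests it. Step 4 of the working rules out the second.

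**Conclusion.** The contradiction between sections 7 and 8.1 is plain on the page. If section 8.1 is followed, allocation is predictable and unconcealed, and the comparison could not properly be reported as randomised. This needs correcting before enrolment, because no later analysis can reliably repair it.

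The documents do not show that steering will occur, and they do not fix its size. Under the stated assumptions (a 25%/75% mix at 40% and 12.4% risk, no true effect, 105 per arm), the chance of a false significant benefit rises from 1.7% to about 5–7% when one in four high-risk patients is steered, and to about 15–19% when one in two is. The range reflects who fills the vacated slot. The direction follows from the mechanism, while the figures belong to the illustration.

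The T0 point is secondary. It rests on inferred order, concerns only EQ VAS, SF-12 and eHEALS, and leaves the primary endpoint and the SPPB baseline untouched. The case for change rests on the alternation alone.

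**What to change.** - In section 8.1, remove the alternating ABAB rule. In section 7, state the same method in the same terms: a computer-generated random sequence concealed from everyone who recruits, held in a web tool or by a consortium partner that does not enrol patients.
- Say whether allocation is by country. Stratifying by country with randomly varying block sizes is one good option and would approximately meet the Table 1 targets. Any properly concealed random sequence cures the main defect.
- Release each assignment only after eligibility, consent and the recruitment-phase assessments are recorded.
- State that the T0 questionnaires are completed before the assignment is disclosed.

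The cost is protocol wording and setting up the list. Sample size stays as planned (power 0.860 at 105 per arm). Placing T0 before disclosure may need some coordination where T0 takes place at home, because the questionnaires and the device delivery may no longer fall together.
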